11.2. Clinical Laboratory Data

The hematology, clinical chemistry, and data will be summarized with descriptive statistics by visit. Both observed values and changes from baseline will be summarized.

A shift table from baseline to Day 15 will be presented for selected clinical laboratory variables based on the reference range-based categories of "Low," "Normal," or "High." A clinical laboratory variable value will be assigned to one of these three categories according to the reference ranges provided by the central clinical laboratory. The shift table will have three rows and three columns, with rows reflecting the reference range category at baseline, and columns reflecting the reference range category at Day 15. A "Total" row and "Total" column will also be included. Subjects with a missing baseline value or who do not have Day 15 data will not be included in the tables for that variable. The number and percentage of subjects in each shift category will be displayed in the table; percentages will be based on the number of subjects included in the table.

The shift table will be presented for the following clinical laboratory variables:

- aspartate aminotransferase (AST),
- alanine aminotransferase (ALT),
- alkaline phosphatase (ALP),
- gamma-glutamyl transferase (GGT),
- total bilirubin,
- creatine kinase,
- creatinine,
- blood urea nitrogen,
- white blood cell count,
- absolute neutrophil count,
- hemoglobin,

• platelet count,

Summaries of sponsor-defined potentially clinically significant (PCS) values will be presented for the following clinical laboratory variables: ALT, AST, creatine kinase, GGT, total bilirubin, white blood cell count, absolute neutrophil count, creatinine, and BUN. The number and percentage of subjects with PCS values that are reported at any postbaseline visit (scheduled or unscheduled) will be summarized. The criteria for identifying PCS clinical laboratory values are provided in Table 3.

Table 3: Potentially Clinically Significant Criteria for Clinical Laboratory Variables

Variable	PCS Threshold
ALT	>3 x ULN (upper limit of normal)
AST	>3 x ULN
Creatine kinase	>5 x ULN
GGT	>3 x ULN
Total bilirubin	>1.5 x ULN
White blood cell count	≤2.8 x 1000/μL
Absolute neutrophil count	<1.5 x 1000/μL
Creatinine	>1.5 x baseline value or > 1.5 x ULN
BUN	>30 mg/dL (> 10.71 mmol/L)

Repeat clinical laboratory samples may be collected at any time during this study due to either missing or abnormal results. The general rule for summarizing these data is to include the original sample results in summary tables. Exceptions to this rule are: (1) all available lab values will be used in the PCS tables and (2) if there are missing results from the original lab samples at screening, the results of a repeat screening sample will be substituted for the missing results in summary tables.

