7.2. Subject Exclusion Criteria

Subjects will be excluded from the study if they:

- 1. Are currently pregnant or lactating.
- 2. Are unable to swallow the study drug capsule.
- 3. Have a clinically significant unstable medical condition or chronic disease (including history of neurological, hepatic, renal, cardiovascular, gastrointestinal, pulmonary, psychiatric or endocrine disease [excluding CAH]), or malignancy that could confound interpretation of study outcome.
- 4. Had a clinically significant illness within 30 days of screening.
- 5. Have a known or suspected differential diagnosis of any of the other known classic forms of CAH including
- 6. Have a history that includes bilateral adrenalectomy, hypopituitarism, or other condition requiring daily therapy with orally administered glucocorticoids (eg, asthma, arthritis, or systemic lupus erythematosus).
- 7. Have any clinically significant acute or unstable chronic abnormal finding in physical examination, neurological assessment, vital signs, ECGs, or clinical laboratory tests, as determined by the investigator.
- 8. Have a history of epilepsy or serious head injury (eg, traumatic brain injury or post-concussive syndrome).

- 9. Have a known history of long QT syndrome or cardiac tachy-arrhythmia.
- 10. Have a screening or Day 1 (baseline) average ECG QT interval corrected for heart rate using Fridericia's correction (QTcF) of >450 msec or the presence of any clinically significant cardiac abnormality.
- 11. Have an exaggerated pharmacological sensitivity (ie, hypersensitivity) to any corticotropin releasing hormone (CRH) antagonists.
- 12. Test positive at screening for hepatitis B surface antigen (HBsAg), hepatitis C antibody (HCV-Ab), or human immunodeficiency virus antibody (HIV-Ab) or have a history of a positive result.

- 18. Have used any other investigational drug within 30 days or 5 half-lives (whichever is longer) before initial screening or plan to use an investigational drug (other than the study drug) during the study.
- 19. Currently use any excluded concomitant medication (refer to Section 8.9.1) and cannot discontinue use of these medications for the duration of the study.

- 20. Have a history of substance (drug or alcohol) dependence or abuse within the 3 months before Day 1 (baseline), as defined in the Diagnostic and Statistical Manual of Mental Disorders (DSM)-IV (Substance Dependence or Abuse) or DSM-5 (Substance Use Disorder).

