Definitions: 17-OHP=17-hydroxyprogesterone; ACTH=adrenocorticotropic hormone; AE=adverse event; C-SSRS=Columbia-Suicide Severity Rating Scale; ECG=electrocardiogram; HBsAg=hepatitis B surface antigen; HCV-Ab=hepatitis C virus antibody; HIV-Ab=human immunodeficiency virus antibody; PD=pharmacodynamic; PK=pharmacokinetic; s=serum; u=urine; UDS=urine drug screen. Footnotes are on the following page.

- ^a Final study visit for subjects who complete the study (or early termination). The final study visit will be conducted approximately 3 weeks (+7 days) after the last dose of study drug.
- ^b Day 1 occurs 1 week after the Day -7 visit. Day 1 assessments will be collected predose unless otherwise noted below. Safety assessments collected predose on Day 1 will serve as the baseline.
- ^c Vital signs will be collected on Days 2 and 15 between 8 and 10 and 22 and 24 hours post-evening dose (ie, morning and evening).
- ^d A standard 12-lead ECG will be conducted in triplicate (1 to 3 minutes apart) after subject has rested supine for at least 5 minutes at screening, pre-evening dose on Days 1 and 14, prior to visit completion or discharge on Days 2 and 15, and at the final study visit (Day 35 or early termination).
- e Pregnancy tests will be conducted for female subjects of childbearing potential. A serum pregnancy test will be conducted at screening, and urine pregnancy tests will be conducted at other timepoints. The pregnancy test will be conducted prior to dosing on Day 1 (for eligibility).
- f Includes hematology, clinical chemistry (including creatine kinase, myoglobin, total and conjugated bilirubin), and urinalysis (including quantitative myoglobin, casts and crystals). Samples will be obtained under nonfasted conditions.
- h Urine testing kits will be provided by the central laboratory to confirm negative drug screen prior to Day -7 PD collection and Day 1 dosing. Separate urine sample will also be sent to the central laboratory for analysis.
- ¹ Blood samples for analyses of 17-OHP, androstenedione, testosterone, cortisol, and ACTH will be collected at the following times:
- Screening (between 0700 and 1000 hours; must be collected prior to first morning dose of hydrocortisone).
- Day -7 to Day -6 (24-hour PD baseline): at approximately 1845, 2000, 2300, 0100, 0300, 0700, 1000, 1500, and 1900 hours.
- Days 1 and 14: 15 minutes pre-evening dose and at 1, 4, and 6 hours post-evening dose (±5 minute window).

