11.3. Vital Signs

The vital signs data, including orthostatic blood pressures and heart rate (calculated as standing value minus supine value), will be summarized with descriptive statistics by visit. Observed and change from baseline values will be summarized.

Summaries of sponsor-defined PCS values will be presented for systolic blood pressure, diastolic blood pressure, and heart rate. The number and percentage of subjects with PCS values that are reported at any postbaseline visit (scheduled or unscheduled) will be summarized. The criteria for identifying PCS vital signs values are provided in Table 4.

Table 4: Potentially Clinically Significant Criteria for Vital Signs Variables

Variable Name	PCS – Low if:		PCS – High if:	
	Observed Value is: AND	Decrease from Baseline is:	Observed Value is: AND	Increase from Baseline is:
Systolic Blood Pressure	<90 mmHg	≥20 mmHg	>180 mmHg	≥20 mmHg
Diastolic Blood Pressure	<50 mmHg	≥15 mmHg	>105 mmHg	≥15 mmHg
Heart Rate	<50 bpm	≥15 bpm	>120 bpm	≥15 bpm

Both supine and standing values of blood pressures and heart rate will be included in the identification and summary of PCS values.

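### The laboratory PCS table does not separate new from pre-existing values, unlike the vital-sign PCS rule in the same SAP

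*SAP*

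**What the plan says.** SAP 11.2 defines the laboratory PCS summary in one sentence: "The number and percentage of subjects with PCS values that are reported at any postbaseline visit (scheduled or unscheduled) will be summarized". Repeat samples are included, because "all available lab values will be used in the PCS tables".

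Table 3 gives the limits. Eight of the nine are absolute (AST, creatine kinase [CK], GGT, total bilirubin, white cell count, neutrophil count, BUN, and ALT, for which the limit is ">3 x ULN (upper limit of normal"). Creatinine alone refers to baseline: ">1.5 x baseline value or > 1.5 x ULN".

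The vital-sign PCS rule in SAP 11.3 is built differently. Table 4 joins an observed limit by AND to a minimum change; its low side carries the column "Decrease from Baseline is".

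Baseline is used elsewhere in SAP 11.2. Changes from baseline are summarized by visit, and "A shift table from baseline to Day 15 will be presented for selected clinical laboratory variables", in Low/Normal/High categories. The variables listed for that shift table include all nine PCS variables.

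For the baseline itself, Protocol Table 2, footnote b, states: "Safety assessments collected predose on Day 1 will serve as the baseline". SAP 6.3.1 agrees. On entry, inclusion criterion 4 asks for good general health judged partly on laboratory tests, and exclusion criterion 7 bars subjects who "Have any clinically significant acute or unstable chronic abnormal finding", as the investigator determines.

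**The concern.** A PCS count is most useful when the reader can tell whether the value arose after dosing began. The laboratory table does not show this. Two subjects with the same postbaseline value, one newly over the limit and one over it throughout, add the same amount to the same row.

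In a controlled trial the comparator would show roughly how much of a row is background. Here there is one arm (Protocol 7.4), about 12 subjects, and safety is the first-listed objective. A single subject visibly moves a row, and nothing in the PCS table says whether that subject was over the limit on Day 1.

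**Working it through.** **1. Figures to reproduce.** None. SAP 4.2 bases the sample size on practical considerations without a power calculation, and no PCS rate is stated. The inputs are the rules in SAP Tables 3 and 4 and N of about 12 (SAP 4.1).

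**2. Unchanged-value test.** Give a subject the same value at baseline and afterwards, and apply each rule.

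| Variable | Baseline = postbaseline | Rule | Counted? |
|---|---|---|---|
| ALT | 3.2 x ULN | > 3 x ULN | Yes |
| CK | 5.5 x ULN | > 5 x ULN | Yes |
| Total bilirubin | 1.7 x ULN | > 1.5 x ULN | Yes |
| Creatinine | 1.6 x ULN | > 1.5 x baseline (ratio 1.0, not met) OR > 1.5 x ULN (met) | Yes |
| Systolic pressure | 88 mmHg | < 90 mmHg (met) AND fall of at least 20 mmHg (0, not met) | No |

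The other five laboratory limits are absolute too, so the result is the same for them. Creatinine's relative limb widens the criterion and does not screen out a pre-existing value. All nine rows can therefore count an unchanged subject; the Table 4 rule cannot.

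**3. What the other laboratory displays show.** Take ALT at a stable 4 x ULN and ALT rising from 1.1 to 4 x ULN. Both exceed 3 x ULN afterwards, so both are PCS. Both are above ULN at baseline and at Day 15, so both sit in the High-to-High cell. The shift table also stops at Day 15, while the PCS count takes in Day 35 and unscheduled values. The by-visit change summaries are group statistics and do not identify which subjects were PCS at baseline.

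**4. Size for one subject.** One unchanged subject and no new case:
- as planned: 1/12 = 8.3% (exact 95% interval 0.2% to 38.5%);
- among subjects not PCS at baseline: 0/11 = 0% (exact upper limit 1 - 0.025^(1/11) = 28.5%).

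The intervals describe sampling uncertainty at this size; they do not measure the misclassification.

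**5. How likely.** The documents give no prevalence of baseline PCS values. Let p be an assumed prevalence for one variable. The chance of at least one such subject among 12 is 1 - (1 - p)^12:

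| Assumed p | Chance of at least one |
|---|---|
| 1% | 11% |
| 2% | 22% |
| 5% | 46% |
| 10% | 72% |

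These chances concern baseline status only. The value must also still be over the limit at a postbaseline sample to enter the count.

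**The case against.** The strongest reply has five parts.

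- **Labeling.** A reader might infer that the table reports pre-existing abnormalities as on-drug events, or gives an on-drug rate that is biased upward. The SAP says neither: it labels the row as postbaseline. The scheduled postbaseline panels fall on Day 15, 24 hours after the last dose, and Day 35, about three weeks after it. This part stands in full.
- **Other displays use baseline.** The shift table and change summaries cover all nine variables, and a stable abnormality that is outside the reference range would show there as High-to-High or Low-to-Low. This stands in part, within the limits shown in step 3 of the working.
- **Eligibility makes the case uncommon.** Inclusion criterion 4 and exclusion criterion 7 act against it, especially for limits of 3 or 5 x ULN. Several exclusion criteria are not visible in the public text, so numeric entry limits can be neither confirmed nor ruled out. It is tempting to add that Day 1 panels go to a central laboratory and may be unread before dosing. That adds little: a persistent abnormality would usually appear at screening, and a transient one would usually be gone by Day 15. What remains is a stable finding that the investigator does not call clinically significant, which the visible criteria do not bar.
- **QTcF is also counted against absolute limits.** SAP 11.5 does this, but its lowest limit is 450 msec and exclusion criterion 10 already bars a Day 1 average above that. The same section adds categories of increase. The parallel does not carry over to the laboratory rows.
- **Over-counting is conservative, and exclusion could hide worsening.** Dropping subjects PCS at baseline would remove a neutrophil fall from 1.4 to 0.5 x 1000/µL from the headline figure. This stands and shapes the remedy: split the count, do not replace it.

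**Conclusion.** The concern holds as a gap in presentation. For all nine variables the laboratory PCS table can count a subject who was already over the absolute limit at baseline and has not changed, and it does not show such subjects separately. The vital-sign rule in the same SAP avoids this. The existing shift table and change summaries repair it only in part.

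The size is 8.3 percentage points per affected subject per row, assuming 12 subjects with postbaseline data. Whether any row is affected depends on a baseline prevalence that the documents do not give, so the figure is illustrative and no bias has been shown. Creatinine's baseline-relative limb should not be read as a precedent for a baseline condition, since it is joined by OR.

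The analysis is descriptive and no decision rule is tied to these rows. Severity: minor; a cheap improvement.

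**What to change.** In SAP 11.2, keep the planned any-postbaseline PCS count and split it by baseline PCS status, with baseline as defined in SAP 6.3.1:

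- (a) the number and percentage with a postbaseline PCS value among subjects who were not PCS at baseline and have at least one postbaseline value;
- (b) a separate column for subjects PCS at baseline, with a listing of their baseline and worst postbaseline values.

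For creatinine, apply the baseline condition to the ULN limb only. The other limb is already a change from baseline, and a baseline value cannot exceed 1.5 times itself. A subject over 1.5 x ULN at baseline who later also exceeds 1.5 x baseline should be marked in the listing under (b).

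The cost is a few lines of SAP text, one extra column and a short listing, all from data already collected, with slightly smaller denominators in affected rows. If the database has already been locked, SAP Section 6 would class the split as post hoc and the study report should label it so.

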11.3. Vital Signs

The vital signs data, including orthostatic blood pressures and heart rate (calculated as standing value minus supine value), will be summarized with descriptive statistics by visit. Observed and change from baseline values will be summarized.

Summaries of sponsor-defined PCS values will be presented for systolic blood pressure, diastolic blood pressure, and heart rate. The number and percentage of subjects with PCS values that are reported at any postbaseline visit (scheduled or unscheduled) will be summarized. The criteria for identifying PCS vital signs values are provided in Table 4.

Table 4: Potentially Clinically Significant Criteria for Vital Signs Variables

Variable Name	PCS – Low if:		PCS – High if:	
	Observed Value is: AND	Decrease from Baseline is:	Observed Value is: AND	Increase from Baseline is:
Systolic Blood Pressure	<90 mmHg	≥20 mmHg	>180 mmHg	≥20 mmHg
Diastolic Blood Pressure	<50 mmHg	≥15 mmHg	>105 mmHg	≥15 mmHg
Heart Rate	<50 bpm	≥15 bpm	>120 bpm	≥15 bpm

Both supine and standing values of blood pressures and heart rate will be included in the identification and summary of PCS values.

11.4. Body Weight

The body weight data (in units of kilograms) will be summarized with descriptive statistics at baseline and each scheduled postbaseline visit. Both observed values and changes from baseline will be summarized.

11.5. Electrocardiogram

The triplicate ECG parameter values recorded at each timepoint for heart rate, PR interval, QRS duration, QT interval, and QTcF (corrected QT interval using Fridericia's formula) interval will be averaged (and rounded to the nearest whole number) for each subject and timepoint for the purpose of statistical summarization. Additionally, for the triplicate investigator overall categorical assessment (ie, Normal, Abnormal not Clinically Significant, or Abnormal Clinically Significant) at each timepoint, the outcome representing the greatest degree of abnormality will be selected for summarization.

Descriptive statistics for the observed values and changes from baseline will be presented for each of the ECG parameters by timepoint.

Frequency tables (number and percentage of subjects) will be presented for the overall categorical assessment at each timepoint.

Two additional categorical summaries (frequency tables displaying number and percentage of subjects) will be presented for the QTcF interval. For the first summary, the observed QTcF values at each timepoint will be classified as follows:

- Greater than 450 msec
- Greater than 480 msec
- Greater than 500 msec

For the second categorical summary, the changes from baseline to each subsequent timepoint will be classified as follows:

- Increase greater than 30 msec
- Increase greater than 60 msec

The same categorical summaries will be presented in frequency tables for values at any postdose timepoint (including unscheduled assessments) meeting the aforementioned criteria.

11.6. Columbia-Suicide Severity Rating Scale

The C-SSRS (Children's Version) data will be presented in the following summaries:

- Screening/lifetime assessment
- Screening/past 1 year assessment
- Baseline (Day 1) assessment
- Postbaseline assessments

Each summary will display the number and percentage of subjects who report "Yes" to specific C-SSRS items or categories of items (a category is assigned a "Yes" value if a "Yes" is reported for any item in the category). These C-SSRS items and categories are as follows:

- Suicidal Ideation Items
 - (1) Wish to be dead
 - (2) Non-specific active suicidal thoughts
 - (3) Active suicidal ideation with any methods (not plan) without intent to act
 - (4) Active suicidal ideation with some intent to act, without specific plan
 - (5) Active suicidal ideation with specific plan and intent
- Suicidal Ideation Category: Any of items (1) through (5)
- Suicidal Behavior Items (not included for screening/past 1 year assessment)
 - (6) Preparatory acts or behavior
 - (7) Aborted attempt
 - (8) Interrupted attempt
 - (9) Non-fatal suicide attempt
 - (10) Completed suicide (not reported for the screening/lifetime assessment)
- Suicidal Behavior Category: Any of items (6) through (10)
- Suicidal Ideation or Behavior Category: Any of items (1) through (10)

For the "all postbaseline assessments" summary, each subject's C-SSRS responses for all postbaseline assessments will be evaluated, and a "Yes" response for any assessment will be considered as a "Yes" for the subject.

In addition to the summaries described above, shift tables comparing postbaseline suicidal ideation scores to baseline scores will be presented. The shift table scores are defined as the following:

- 0 = No suicidal ideation
- 1 =Wish to be dead
- 2 = Non-specific active suicidal thoughts
- 3 = Active suicidal ideation with any methods (not plan) without intent to act
- 4 = Active suicidal ideation with some intent to act, without specific plan

5 = Active suicidal ideation with specific plan and intent

The shift tables will display the number and percentage of subjects within each cell of a 6 x 6 table for each treatment group, with the rows representing the baseline score and the columns representing the maximum score recorded across all postbaseline assessments (including both scheduled and unscheduled visits). Subjects missing either a baseline score or all postbaseline scores will not appear in the table.

11.7. Brief Psychiatric Rating Scale for Children

The Brief Psychiatric Rating Scale for Children (BPRS-C) includes 21 items and the severity of each item is rated on a 7-point scale (1=not present, 2=very mild, 3=mild, 4=moderate, 5=moderately severe, 6=severe, 7=extremely severe). The BPRS-C total score is calculated as the sum of the scores for the 21 items (total score range: 21 to 147). If any one of the 21 items is not scored (ie, has a missing value), the BPRS total score will be set equal to missing.

BPRS total score observed values and change from baseline values will be summarized with descriptive statistics by visit.

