8.5.5. Brief Psychiatric Rating Scale for Children

The Brief Psychiatric Rating Scale for Children (BPRS-C) was created to provide a concise profile of childhood behavioral and emotional symptomatology (Hughes et al., 2001; Overall and Pfefferbaum, 1982). The BPRS-C includes 21 items that assess behavioral problems, depression, thinking disturbance, psychomotor excitation, withdrawal, anxiety, and organicity. The severity of each of the 21 items of the BPRS-C is rated on a scale of 0 (not present) to 6 (extremely severe) (total score range: 0 to 126). Higher scores represent greater symptom severity.

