2. INTRODUCTION

The purpose of this statistical analysis plan (SAP) is to describe the planned analyses and data displays that will be prepared to summarize the data from the Phase 2 study described in Neurocrine Biosciences, Inc. (NBI) Protocol NBI-74788-CAH2008.

This SAP was developed in accordance with ICH (International Council for Harmonisation of Technical Requirements for Pharmaceuticals for Human Use) E9 guidance. All decisions regarding the final analysis, as defined in this SAP document, will be made prior to database lock. Changes made to the planned analyses after finalization of this SAP and database lock will be described in the clinical study report (CSR). Further information related to study design and methodology can be found in the protocol.

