12. DEVIATIONS FROM PROTOCOL PLANNED ASSESSMENTS AND ANALYSIS

13. PERFORMANCE QUALIFICATION OF SAS® PROGRAMS

The analysis and summary of data from this study will be performed using $SAS^{\$}$ 9.4 (or a later release if available). All $SAS^{\$}$ programs used in the production of statistical analyses, tables, listings, and figures described in this SAP will undergo performance qualification (verification that the program produces the intended output) in accordance with department standard operating procedures. The performance qualification may include independent programming and/or peer review of the $SAS^{\$}$ log files. In addition, tables, figures, listings, and statistical analysis output will be independently reviewed for completeness and accuracy.

14. **REFERENCES**

European Medicines Agency. Points to consider on implications of Coronavirus disease (COVID-19) on methodological aspects of ongoing clinical trials. March 2020.

United States Food and Drug Administration. Conduct of Clinical Trials of Medical Products During the COVID-19 Public Health Emergency. Guidance for Industry, Investigators, and Institutional Review Boards. March 2020, updated January 2021.

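### Does the one-point difference in BPRS-C item coding between Protocol 8.5.5 and SAP 11.7 affect the safety analysis?

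*SAP*

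**What the plan says.** Protocol 8.5.5 describes the instrument. It states that "The BPRS-C includes 21 items that assess behavioral problems, depression, thinking disturbance, psychomotor excitation, withdrawal, anxiety, and organicity", and that each item is "rated on a scale of 0 (not present) to 6 (extremely severe) (total score range: 0 to 126").

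SAP 11.7 also has 21 items, but each is "rated on a 7-point scale (1=not present, 2=very mild, 3=mild, 4=moderate, 5=moderately severe, 6=severe, 7=extremely severe"). The scoring rule follows: "The BPRS-C total score is calculated as the sum of the scores for the 21 items (total score range: 21 to 147"). A total with any item missing is itself set to missing. On reporting, "BPRS total score observed values and change from baseline values will be summarized with descriptive statistics by visit".

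Neither document shows a rule for converting one coding to the other. SAP section 12, headed "DEVIATIONS FROM PROTOCOL PLANNED ASSESSMENTS AND ANALYSIS", has no text under its heading in the public copy. That may be a redaction, so a note on the difference may exist there.

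**The concern.** The two descriptions cannot both match what was recorded. The eCRF holds one numbering of the seven levels, and under the other document the stated range and end anchors are wrong.

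BPRS-C is a listed safety assessment in both documents, safety and tolerability is the first-listed objective, and the SAP reports observed totals as well as changes. A reader who takes the scale from the protocol and the table from the SAP could misread the level. A total of 21 means no symptoms on the SAP scale. On the protocol scale it means an average of one level above the lowest anchor on every item. If the eCRF stored 0 to 6 and the SAP's sum were applied as written, totals below the SAP's stated minimum could appear.

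**Working it through.** **Inputs.** Number of items: 21 in both documents. Item levels: 0 to 6 (Protocol 8.5.5) and 1 to 7 (SAP 11.7), seven in each case, with the same two end anchors. Missing-item rule (SAP 11.7): no total unless all 21 items are scored.

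**Stated ranges.** Range = items × lowest level to items × highest level.

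- Protocol: 21 × 0 = 0 to 21 × 6 = 126.
- SAP: 21 × 1 = 21 to 21 × 7 = 147.

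Both ranges reproduce, so each document is consistent with itself. The difference is one of item coding, not an arithmetic slip.

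**Size of the shift.** The protocol names only the end anchors. With seven ordered levels and identical ends, the only one-to-one mapping that keeps the order is level k in the protocol to level k + 1 in the SAP. Because every total has all 21 items:

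SAP total = protocol total + 21 × 1 = protocol total + 21.

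A check on 100,000 simulated pairs of 21-item profiles gave 21 as the only difference in totals and 0 as the only difference in change from baseline.

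**Effect on each planned summary, under one coding throughout.**

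- Observed mean, median, minimum and maximum: each moves by 21.
- SD and SE: unchanged, because adding a constant leaves deviations from the mean as they were.
- Change from baseline: (T2 + 21) − (T1 + 21) = T2 − T1, so unchanged. For example, protocol totals of 10 and then 5 become 31 and 26; the change is −5 either way.
- Percent change would depend on the coding, because the denominator moves by 21. SAP 6.4.2 defines percent change in general, but SAP 11.7 does not call for it here.

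**Other uses of the total.** In the visible text there are none. Protocol 8.10.1 lists no BPRS-C criterion for withdrawal. SAP 11.7 sets no threshold and no responder category, and the study is descriptive with no formal test.

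**Can the coding be read from the data?** Yes, in most plausible cases. A single item recorded as 0 shows the 0-to-6 coding, and a single item recorded as 7 shows the 1-to-7 coding.

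**The case for a change.** The strongest case for a change is that observed safety scores should be readable without guesswork. BPRS-C has its own row in the SAP's table of data summaries by analysis set. SAP section 2 sends readers to the protocol for methodology, where they find a different scale. Low-symptom totals on the SAP coding, such as 21 to 41, are also valid protocol totals, where they would indicate real symptoms. Counting possible values, 126 − 21 + 1 = 106 of the 127 totals on either scale are valid on both. The remedy would also be cheap.

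Part of this stands. The mismatch is genuine, it is not a PDF artefact, and someone comparing observed totals with the protocol's range could misread them.

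The rest is weaker.

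- The count of 106 treats all totals as equally likely. The protocol requires good general health and excludes subjects whose clinically significant unstable or chronic disease, psychiatric disease included, could confound the results, as well as those at significant risk of suicidal or violent behavior. Scores near the floor are therefore plausible. On 0-to-6 coding such totals lie between 0 and 20, which cannot occur on the SAP scale, and the SAP reports the minimum.
- There are not two competing analyses. Protocol 8.5.5 describes the scale, and Protocol section 12 leaves detailed summaries to the SAP. The SAP is the later document (October 2021 against May 2019), prints all seven anchors and states the scoring rule.
- SAP section 13 already provides for program qualification and independent review of outputs. A total below the SAP's own stated minimum would be a plain failure at that step.

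**Conclusion.** The concern is correct as a matter of text and has no consequence for the analysis. The two documents differ by 1 per item and 21 per complete total. That affects only the level at which observed totals are labelled and read. Change from baseline, SD and the safety conclusion differ by 0. Correcting the text would align a sentence and a table label without altering a result, so no change to the plan follows.

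This rests on three assumptions. One coding was used for all ratings; nothing in the documents suggests otherwise, but a subject rated on different codings at two visits would show a spurious change of 21 points. The two sets of levels correspond in order, as their shared end anchors imply. The analyst confirms the stored item values before summing, as is routine when a scored scale is programmed. The public documents do not show which coding the eCRF used, and the conclusion does not depend on it.
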